6.6.3 Dose modifications

For participants who do not tolerate the protocol-specified dosing schedule, dose interruptions, and/or reductions are either recommended or mandated in order to allow participants to continue the study treatment.

Table 6-3 Dose reduction schedule

*Dose reduction			
		Starting dose level 0	Dose level – 1
Asciminib	CML-CP	40 mg b.i.d. (total daily dose 80 mg)	20 mg b.i.d. (total daily dose 40 mg)
	CML-CP	80 mg q.d. (total daily dose 80 mg)	40 mg q.d. (total daily dose 40 mg)
	CML-CP	200 mg q.d. (total daily dose 200 mg)	80 mg q.d. or 40 mg b.i.d. (total daily dose 80 mg)**
*Dose reduction should be based on the worst toxicity demonstrated at the last dose.			
**Patients on 200 mg q.d. needing a dose de-escalation will revert to 80 mg total daily dose of asciminib, according to pre-escalation dosing schedule (q.d. or b.i.d. regimen assigned at enrollment).			
Asciminib dose reduction below total daily dose of 40 mg (20 mg b.i.d. or 40 mg q.d.) is not allowed. 20 mg tablets will be dispensed to patients having 20 mg b.i.d. regimen in the instance of dose reduction.			

These dose modifications, in addition to permanent treatment discontinuations, are summarized in (Table 6-4). Deviations to mandatory dose interruptions and/or reductions are not allowed.

These dose changes must be recorded on the appropriate CRF.

A patient must discontinue treatment with asciminib if, after treatment is resumed at a lower dose level, the toxicity recurs with the same or worse severity, except for recurrence of cytopenias (Table 6-4). If a patient requires a dose interruption of > 28 days for each non-hematologic toxicity, then the patient must be discontinued from the study treatment. If a hematologic toxicity (cytopenia Grade 3 or 4) last for more than 42 days without recovery to at least a Grade 2, despite asciminib interruption and adequate management (including hematopoietic growth factors), then the patient must be discontinued from study treatment.

Table 6-4 Criteria for dose reduction / interruption / discontinuation and re-initiation of treatment for adverse drug reactions

Dose modifications for asciminib	
Please note that if a patient requires a dose interruption of > 28 days for any toxicity, and > 42 days for hematologic toxicity, then the patient should be discontinued from study treatment	
Worst toxicity CTCAE Version 5.0	Asciminib

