Investigations (hematologic): If a hematologic toxicity (cytopenia grade 3 or 4) lasts for more than 42 days without recovery to at least grade 2, despite asciminib interruption and adequate management (including hematopoietic growth factors), then the patient should be discontinued from study treatment.	
Neutropenia (ANC)	
Grade 1 (ANC < LLN – 1.5 x 10 ⁹ /L)	Recommendation: Maintain dose level
Grade 2 (ANC < 1.5 – 1.0 x 10 ⁹ /L)	Recommendation: Maintain dose level
Grade 3 (ANC < 1.0 – 0.5 x 10 ⁹ /L)	Mandatory: Hold dose until resolved to grade ≤ 2 (recheck CBC 2x/week), then: if resolved in ≤ 14 days, then maintain dose level If resolved in > 14 days, then reduce dose ↓ 1 dose level
Grade 4 (ANC < 0.5 x 10 ⁹ /L)	Mandatory: Hold dose until resolved to grade ≤ 2, (recheck CBC 2x/week), then: if resolved in ≤ 14 days, then maintain dose level if resolved in > 14 days, then reduce dose ↓ 1 dose level

Dose modifications for asciminib	
Please note that if a patient requires a dose interruption of > 28 days for any toxicity, and > 42 days for hematologic toxicity, then the patient should be discontinued from study treatment	
Worst toxicity CTCAE Version 5.0	Asciminib
Febrile neutropenia (ANC < 1.0 x 10 ⁹ /L, fever ≥ 38.5°C)	Mandatory: Hold dose until resolved, then reduce dose ↓ 1 dose level
Thrombocytopenia	
Grade 1 (PLT < LLN – 75 X 10 ⁹ /L)	Recommendation: Maintain dose level
Grade 2 (PLT < 75 - 50 x 10 ⁹ /L)	Recommendation: Maintain dose level
Grade 3 (PLT < 50 - 25 x 10 ⁹ /L)	Mandatory: Hold dose until resolved to grade ≤ 2 (recheck CBC 2x/week), then: if resolved in ≤ 14 days, then maintain dose level if resolved in > 14 days, then reduce dose ↓ 1 dose level
Grade 4 (PLT < 25 x 10 ⁹ /L)	Mandatory: Hold dose until resolved to grade ≤ 2 (recheck CBC 2x/week), then: if resolved in ≤ 14 days, then maintain dose level if resolved in > 14 days, then reduce dose ↓ 1 dose level
Recurrence of any cytopenia	Recommendation: Hold dose until resolved to grade ≤ 2, then maintain current dose level For recurrent Grade 3/4 cytopenia, please refer to above guidelines for neutropenia and thrombocytopenia; no further dose reduction is allowed for already reduced dose.
Non-hematologic adverse reactions except where further specified in individual sections	
Grade 1	Recommendation: Maintain dose level
Grade 2	Recommendation: Hold dose until resolved to grade ≤ 1, then maintain dose level
Grade 3	Mandatory: Hold dose until resolved to grade ≤ 1, then reduce dose ↓ 1 dose level

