2.5.3 Handling of intercurrent events

The approach of accounting for intercurrent events is as follows:

- **For the intercurrent events 4a:** The composite strategy will be applied for treatment discontinuation due to any reason. Treatment discontinuations due to any reason will be defined as non-responders.
- **For the intercurrent events 4b:** The treatment policy strategy will be applied. Meaning, the actual values of the variable (BCR::ABL1 % IS) will be used, regardless of whether the intercurrent event has occurred.
- **For the intercurrent events 4c:** The treatment policy strategy will be applied. Meaning, the actual values of the variable (BCR::ABL1 % IS) will be used, regardless of whether the intercurrent event has occurred.

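### Protocol 6.6.3 and Table 6-4 word the maximum-interruption stopping rule differently in scope, clock and force; the passages should be reconciled, as a minor point

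*Protocol*

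**What the plan says.** The rule on how long dosing may be held before treatment must end appears three times in Protocol Section 6.6.3.

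- **Running text.** For non-hematologic toxicity: "If a patient requires a dose interruption of > 28 days for each non-hematologic toxicity, then the patient must be discontinued from the study treatment". For hematologic toxicity the trigger is different: "If a hematologic toxicity (cytopenia Grade 3 or 4) last for more than 42 days without recovery to at least a Grade 2", despite interruption and adequate management. Here too the patient *must* be discontinued.
- **Table 6-4 header**, repeated on each page of the table: "Please note that if a patient requires a dose interruption of > 28 days for any toxicity, and > 42 days for hematologic toxicity". The stated consequence is that treatment *should* end.
- **Table 6-4, opening row of the hematologic block.** "If a hematologic toxicity (cytopenia grade 3 or 4) lasts for more than 42 days without recovery to at least grade 2", with the consequence worded as *should*.

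Protocol Section 9.1.1 lists circumstances in which treatment must be discontinued. For adverse events and their recurrence it refers to Table 6-4, not to the 6.6.3 text.

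The endpoint consequence is set in SAP Section 2.5.3 for discontinuation before Week 48: "Treatment discontinuations due to any reason will be defined as non-responders". Protocol Section 12.4.3 reaches the same result for discontinuation due to intolerance. Under both documents, a patient whose dose is only interrupted keeps the observed Week 48 BCR-ABL1 value.

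**The concern.** The three statements differ in three respects.

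1. **Scope of the 28-day limit.** The text restricts it to non-hematologic toxicity. The header attaches it to *any* toxicity, which taken literally includes cytopenia.
2. **Clock for the 42-day limit.** The header counts days of dose interruption. The text and the hematologic row count days of grade 3/4 cytopenia without recovery to grade 2.
3. **Force.** The text says *must*. The header and the hematologic row say *should*. Section 9.1.1 then refers a *must* to the table that says *should*.

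This rule ends a patient's treatment, so sites need to apply it in the same way. It also feeds the primary endpoint: a patient stopped before Week 48 is a non-responder whatever the molecular result would have been, while a patient kept on treatment is scored on the observed value.

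**Working it through.** **The passages side by side**

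| Source | 28-day limit covers | 42-day clock | Force |
|---|---|---|---|
| 6.6.3 text | non-hematologic toxicity | duration of grade 3/4 cytopenia not recovered to grade 2 | must |
| Table 6-4 header | any toxicity | length of dose interruption | should |
| Table 6-4 hematologic row | not stated | duration of grade 3/4 cytopenia not recovered to grade 2 | should |

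**Test case 1: dosing held 29 to 42 days for cytopenia.** The text, the hematologic row and the header's second clause all leave the patient on treatment. Only the header's first clause, with *any* taken literally, stops the patient.

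**Test case 2: febrile neutropenia.** Table 6-4 requires a hold until the event resolves, not until neutrophils reach grade 2. The hold could pass 42 days after the count has recovered to grade 2. The header's clock is then exceeded and the clock in the text and row is not.

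**Test case 3: cytopenia that began before the hold.** The cytopenia can exceed 42 days while the interruption is shorter. The text and row are then triggered and the header is not.

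Cases 2 and 3 do not depend on how *any* is read.

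**The plan's own figure.** Inputs from Protocol Section 12.8.1: n = 156, null rate 0.23, alternative 0.33, one-sided level 0.025, exact test.

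- The smallest r with P(X ≥ r | 156, 0.23) ≤ 0.025 is r = 47. The exact level is 0.0241; at r = 46 it would be 0.0363.
- Power = P(X ≥ 47 | 156, 0.33) = 0.801. The stated 80% is reproduced.

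No numerical error is at issue.

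**Illustration of the endpoint effect.** The documents do not say how many patients would have holds on which the wordings disagree. To choose a count m, take the 17.3% rate of grade 3 or higher thrombocytopenia reported for asciminib in the earlier phase III trial (Protocol Section 1.1): 0.173 × 156 = 27.0. If 10% to 20% of these patients had such a hold before Week 48 (an assumption with no source in the documents), m would be 2.7 to 5.4, or about 3 to 5.

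Suppose these m patients would otherwise respond at 33% like the rest, and all are stopped. They become certain non-responders, so power = P(X ≥ 47 | 156 − m, 0.33).

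| m stopped | Expected responders lost (0.33 × m) | Power | Loss (points) |
|---|---|---|---|
| 0 | 0 | 80.1% | 0 |
| 1 | 0.33 | 78.5% | 80.1 − 78.5 = 1.6 |
| 3 | 0.99 | 75.2% | 80.1 − 75.2 = 4.9 |
| 5 | 1.65 | 71.5% | 80.1 − 71.5 = 8.6 |

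The loss tends to zero as m does, and it is smaller if only some sites stop these patients.

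**The case against.** The strongest objection is that the header already agrees with the text. If *any* toxicity included cytopenia, every hematologic hold would end at 28 days and the header's 42-day clause could never operate. A general limit followed by a hematologic exception is the natural reading. The hematologic row, which opens that block of the table, also gives 42 days. This stands. A reader might infer that the protocol gives two equally valid answers, 28 or 42 days, for a cytopenia hold. The documents do not support that: the conflict on the limit rests on one word.

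A second objection is that the two clocks nearly coincide. For grade 3/4 neutropenia and thrombocytopenia, dosing is held until grade 2 or better with blood counts twice weekly, so the hold and the unrecovered cytopenia cover nearly the same days. This holds for most cases. It does not cover febrile neutropenia, which is held to a different end point, or cytopenia present before the hold began.

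A third objection concerns force. A reader might cite the 6.6.3 sentence forbidding deviations as making *should* in the table more serious. That sentence covers mandatory interruptions and reductions, not permanent discontinuation, so it adds nothing here. The plain difference between *must* and *should* remains.

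Finally, the same passage that reports 17.3% thrombocytopenia says only 5 patients (3.2%) discontinued for it, and Protocol Section 1.2 expects a less advanced population here. Both argue against a large effect, though neither gives the number of long holds.

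**Conclusion.** The inconsistency is real but minor. The text, header and hematologic row differ in literal scope, in what is timed and in force, and Section 9.1.1 directs mandatory discontinuation to the table. On the limits, the natural reading of the header matches the text. The clock and the force remain inconsistent under any reading.

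The effect on the primary endpoint is unquantified and probably small. The loss of about 5 to 9 power points is an illustration. It assumes three to five affected patients, all stopped before Week 48, each with a 33% chance of response had treatment continued. A reader might infer a larger effect by treating every affected patient as a lost responder. Nothing in the documents supports that, and the number affected is itself assumed. A stop after Week 48 does not change the primary endpoint, although the wording still bears on whether that patient stays on treatment. The planned sample size, significance level and power calculation are unaffected.

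**What to change.** Reconcile the Table 6-4 header, the hematologic row of that table and the 6.6.3 text. All three should state the same limit for each toxicity class, the same clock (length of interruption or duration of the toxicity) and the same force (*must* or *should*). The wording should also settle how the rule applies to febrile neutropenia and to cytopenia that began before the hold. Section 9.1.1 can keep its reference once the table is consistent. The sponsor's clinical team decides the values; no view is offered here on which is right.

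The cost is a wording clarification through a protocol amendment. It adds no visits, procedures or data collection and changes nothing in the sample size or the primary test.

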Tele-visit	Procedures or communications conducted using technology such as telephone or video-conference, whereby the participant is not at the investigative site where the investigator will conduct the trial.
Variable (or endpoint)	The variable (or endpoint) to be obtained for each participant that is required to address the clinical question. The specification of the variable might include whether the participant experiences an intercurrent event.
Withdrawal of study consent (WoC) / Opposition to use of data /biological samples	
Withdrawal of consent from the study occurs when the participant explicitly requests to stop use of their data and biological samples (opposition to use data and biological samples) AND no longer wishes to receive study treatment AND does not agree to further protocol required assessments. This request should be in writing (depending on local regulations) and recorded in the source documentation.
 
Opposition to use data/biological samples occurs in the countries where collection and processing of personal data is justified by a different legal reason than consent.

Amendment 01 (10-Aug-2022)

Amendment rationale

As of 10 August 2022, 111 patients have been screened in the study and 91 patients have been randomized and received treatment. The study is ongoing.

The main purpose of this protocol amendment is to:

Implement UK and Canada local protocols amendment changes within the global protocol

- Add an exclusion criterion for recent participation in an interventional trial and clarify the IMP wash-out period required for study participation
- Include guidance in [Table 6-4](#) regarding dose withholding in patients, who experience 5- to 20-fold ULN transaminase elevations while taking asciminib and dose modifications guidelines for patients having elevated levels at baseline.
- [Table 6-5](#) added regarding Clinical and diagnostic assessments to rule out possible alternative causes of observed LFT abnormalities
- Clarify the guidance regarding dose modification criteria for recurrence of grade 3/4 cytopenia and to elaborate the guidance for follow up of a participant having potential drug-induced liver injury during the study.
- Implement editorial changes throughout the protocol to correct typos and provide clarifications where required.

Information on FDA marketing authorization for asciminib has been added.

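### Table 6-4, recurrent cytopenia: for a slow grade 3/4 recurrence at an unreduced dose, the row's two sentences give different restart doses (minor; the second sentence should govern)

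*Protocol*

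**What the plan says.** All the relevant text is in Protocol Section 6.6.3 and its Tables 6-3 and 6-4, with the background in the Amendment 01 rationale.

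- **Recurrence row, sentence 1:** "Recommendation: Hold dose until resolved to grade ≤ 2, then maintain current dose level". It has no condition on recovery time.
- **Recurrence row, sentence 2:** "For recurrent Grade 3/4 cytopenia, please refer to above guidelines for neutropenia and thrombocytopenia; no further dose reduction is allowed for already reduced dose".
- **Neutropenia and thrombocytopenia rows, grade 3 and 4:** labelled mandatory. Drug is held until grade 2 or better. The dose is kept if recovery takes 14 days or less; otherwise "If resolved in > 14 days, then reduce dose ↓ 1 dose level".
- **Febrile neutropenia row:** "Mandatory: Hold dose until resolved, then reduce dose ↓ 1 dose level". Recovery time plays no part.
- **Grade 1 and 2 rows:** keep the dose, with no hold.
- **Long cytopenia:** treatment stops if a grade 3 or 4 cytopenia "lasts for more than 42 days without recovery to at least grade 2".
- **Force of the mandatory rows:** "Deviations to mandatory dose interruptions and/or reductions are not allowed".
- **Floor:** "Asciminib dose reduction below total daily dose of 40 mg (20 mg b.i.d. or 40 mg q.d.) is not allowed".
- **Amendment 01, stated purpose:** "Clarify the guidance regarding dose modification criteria for recurrence of grade 3/4 cytopenia".

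**The concern.** A site managing a recurrent cytopenia is sent to this row: Section 6.6.3 exempts recurrent cytopenias from the general rule to discontinue when a toxicity recurs, and refers to Table 6-4 instead. The first instruction found there is to restart at the current dose. The second leads to rows that may require a lower one. A site that acts on the first sentence alone, after a recurrence that was slow to recover, restarts one level too high and departs from a mandatory reduction.

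What is at stake is the restart dose after a prolonged grade 3/4 cytopenia, and consistent practice between sites. The hold during the cytopenia and the 42-day stopping rule apply under either sentence.

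**Working it through.** No sample-size or error-rate figure is involved. The check sets the two sentences side by side for each situation.

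**Step 1. Which events does sentence 1 reach?** The grade 1 and 2 rows for neutropenia and thrombocytopenia contain no hold, and holding until grade 2 or better does nothing for an event that is already grade 1 or 2. For these two cytopenias sentence 1 can therefore act only on grade 3/4 events, which are the events sentence 2 covers. The sentences cannot be separated by grade.

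**Step 2. Restart dose for a recurrence** (total daily dose; one level down taken from Table 6-3)

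| Dose at recurrence | Recovery | Sentence 1 | Rows named in sentence 2 | Result |
|---|---|---|---|---|
| 80 mg, not reduced | ≤ 14 days | 80 mg | 80 mg | agree |
| 80 mg, not reduced | > 14 days | 80 mg | 40 mg | differ |
| 200 mg, escalated | ≤ 14 days | 200 mg | 200 mg | agree |
| 200 mg, escalated | > 14 days | 200 mg | 80 mg | differ |
| 40 mg, already reduced | any, within the 42-day limit | 40 mg | 40 mg | agree |
| 80 mg after de-escalation from 200 mg | > 14 days | 80 mg | 80 mg if this counts as already reduced, otherwise 40 mg | unclear |

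**Step 3. Example.** A patient on 80 mg has a first grade 3 thrombocytopenia that clears in 10 days. Since 10 ≤ 14, the dose stays at 80 mg. It recurs at grade 3 and takes 20 days to recover, which is more than 14 and less than 42. Sentence 1 restarts at 80 mg; the thrombocytopenia row reached through sentence 2 restarts at 40 mg.

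**Step 4. Febrile neutropenia.** A first febrile episode after an earlier afebrile neutropenia would also give 80 mg against 40 mg if it were treated as a recurrence under sentence 1. But febrile neutropenia has its own mandatory row, and a first febrile episode falls naturally under that row. This is a secondary example only.

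**Step 5. How many patients?** The only documented rate that helps is 17.3% for grade 3 or higher thrombocytopenia on asciminib in ASCEMBL (Protocol Section 1.1). If it carried over, first events would number about 0.173 × 156 = 27.0 in the primary population, or 0.173 × 186 = 32.2 in all patients. The overlap concerns only those who then have a grade 3/4 recurrence, at an unreduced dose, with recovery beyond 14 days. The documents give none of those three shares, and no neutropenia rate to add.

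**The case against.** The strongest reply is that the row settles the matter itself. Sentence 2 addresses exactly the disputed case, is more specific than the default before it, and points to mandatory rows, whereas sentence 1 is labelled a recommendation. Section 6.6.3 supplies the tie-break by forbidding deviation from mandatory reductions, and Amendment 01 states that it meant to clarify this very guidance. Sentence 1 also keeps a coherent role for patients already at 40 mg and for cytopenias with no row of their own, such as anaemia. A general default followed by a specific exception is ordinary drafting.

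Most of this stands. It fixes which sentence should govern, and it means that a wrong restart dose requires a site to overlook sentence 2. It does not remove the contradiction: the row nowhere states the precedence, and sentence 1 comes first, covers any cytopenia, and is not limited to the two situations in which it does no harm.

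Three stronger readings are tempting, and the documents do not support them:

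- A reader might infer that the protocol directs sites to overdose after recurrent cytopenia. Read as a whole, the row does not.
- A reader might infer that febrile recurrences are an equal second conflict. Their own mandatory row already covers them.
- A reader might try to derive a maximum number of affected patients by requiring a fast first event followed by a slow recurrence. That fails because Section 6.6.2 contemplates patients reduced to 40 mg who later spend at least 3 months back on 80 mg. A slow first event, a return to 80 mg and a slow recurrence meets the same contradiction.

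**Conclusion.** The point holds as a minor leftover contradiction in a dosing-safety rule. For a grade 3/4 neutropenia or thrombocytopenia that recurs at an unreduced dose and takes more than 14 days to recover, the row literally yields two restart doses: 80 or 40 mg, and 200 or 80 mg after escalation. Sentence 2 is the better reading.

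The number of patients is likely small, because three conditions must coincide within a group that is itself a minority. That is a judgement: it rests on the ASCEMBL thrombocytopenia rate being a fair guide. Any count would also be of patients for whom the wording overlaps, and the documents give no basis for estimating how many would actually be misdosed.

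A reader might also look for an effect on the primary result. There is none on the analysis, power or significance level: dose modification and interruption are handled by treatment policy (Protocol Section 12.4.3, SAP Section 2.5.3), so the observed week-48 value is used whichever dose was restarted.

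Confidence is high that the wording conflicts. The documents do not show whether any site would act on the wrong sentence.

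**What to change.** Reword the recurrence row as follows.

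1. Limit sentence 1 to recurrence at an already reduced dose and to cytopenias with no row above, such as anaemia.
2. State that, at an unreduced dose, recurrent grade 3/4 neutropenia or thrombocytopenia, and febrile neutropenia, follow their mandatory rows as for a first event. This includes the one-level reduction when recovery takes more than 14 days.
3. Keep the bar on further reduction of an already reduced dose, and say whether 80 mg reached by de-escalation from 200 mg counts as already reduced. Table 6-3 lists it as one level below 200 mg, but it is also the standard starting dose, so the present text can be read either way.
4. Keep the hold for grade 3/4 neutropenia and thrombocytopenia and for febrile neutropenia mandatory at every dose, and keep the febrile hold running until resolution. Otherwise, limiting sentence 1 to reduced doses could be taken to make the hold there only a recommendation, or to end a febrile hold at grade 2.

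The cost is the wording of one table row in the next protocol amendment. It needs no extra assessments and no change to the SAP.
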